## PFIZER GENERAL BUSINESS

# 3.2. Secondary Endpoint(s)

## 3.2.1. Response based on IGA Score

The Investigator's Global Assessment of AD is scored on a 5-point scale (0-4), reflecting a global consideration of the erythema, inducation and scaling (Appendix 2.2). Response is defined as a Week 12 score of clear (0) or almost clear (1), which also translates to a reduction of at least 2 points from baseline.

## 3.2.2. Response based on EASI-75

The EASI quantifies the severity of a subject's atopic dermatitis based on both severity of lesion clinical signs and the percent of body surface area (BSA) affected (Appendix 2.3). Response is defined as improvement of at least 75% from baseline in the EASI total score at Week 12.

## 3.2.3. Response based on SCORAD75

The SCORAD is a validated scoring index for AD, which combines extent (0-100), severity (0-18), and subjective symptoms (0-20) based on pruritus and sleep loss, each scored using a visual analog scale (0-10). The SCORAD total score for an individual ranges from 0 to 103 (Appendix 2.4). The extent score is set to missing if any of the body areas are missing. The severity score is set to missing if severity is missing for any of the subjective symptoms. The subjective symptom score is set to missing if either the itch score or the sleeplessness score is missing. The total score is set to missing if any of the 3 components is missing. Response is defined as improvement of at least 75% from baseline in the SCORAD total score at Week 12.

## 3.2.4. Change from baseline in POEM Score

The POEM is a validated 7-item patient-reported outcome (PRO) measure used to assess the impact of AD recalled over the past week. Each item is scored from 0 (No days) to 4 (Every day). The POEM score is derived as the sum of scores from all 7 POEM items. The range of POEM score is 0 to 28, with higher scores indicating greater symptom burden. If one item is unanswered, this is scored as 0. If two or more items are unanswered, the POEM score is set to missing. Change from baseline in POEM score is derived for all scheduled time points. A positive mean change score indicates worsening of symptom burden over time.

## 3.2.5. Change from baseline in ADCT Score

The ADCT is a validated 6-item PRO measure used to assess patient-perceived AD control. Each item is scored 0 to 4. The ADCT score is derived as the sum of scores from all 6 ADCT items. The range of ADCT score is 0 to 24, with higher scores indicating lower AD control. If one item is unanswered, the ADCT score is set to missing. Change from baseline in ADCT score is derived for all scheduled time points. A positive mean change score indicates worsening of AD control over time.

PFIZER GENERAL BUSINESS

# 3.3. Other Endpoint(s)

The following additional endpoints will be derived for participants included in the substudy.

## 3.3.1. Incidence of Bone Safety Findings

The primary substudy endpoint is the incidence of bone safety findings in knee MRI after 1 year of being exposed to abrocitinib in adolescent participants 12 to <18 years of age. Bone safety findings will be adjudicated by the Safety Adjudication Committee.

## 3.4. Baseline Variables

For all safety and efficacy analyses, baseline value is defined as the result of the last assessment performed prior to first dose of study treatment.

### 3.5. Safety Endpoints

#### 3.5.1. Adverse Events

See Section 3.1.

## 3.5.2. Laboratory Data

Below is a list safety laboratory data that will be collected in the study. Change from baseline will be derived for laboratory parameters with scheduled post-baseline assessments.

Hematology	Chemistry	Lipid Profile a	Other
Hemoglobin	Urea	Total cholesterol	At screening only:
WBC count	sCr	LDL	• FSH b
Neutrophils (%, Abs)	sCysC (at Screening)	VLDL	• Serum pregnancy test
Lymphocytes (%, Abs)	Estimated Creatinine	HDL	(β-hCG, for WOCBP
Platelets	Clearance	Triglycerides	only) c
Coagulation Panel	AST		• HBsAg
(APTT, PT/INR)	ALT		• HIV
	TBili		• HCV
	Alkaline phosphatase		• TB test (as per site
			standards)

 Table 2.
 Protocol-Required Safety Laboratory Assessments

a. Fasting lipid profile panel require at least an 8 hour fast. If possible, participants should comply with fasting requirements at those visits detailed above.

b. For confirmation of postmenopausal status only.

c. Urine pregnancy test (for WOCBP only) will be performed at all visits other than screening visits.

# 3.5.3. Vital Signs

Vital signs data include blood pressure and pulse rate.

#### PFIZER GENERAL BUSINESS

## 3.5.4. Electrocardiograms

Electrocardiograms (ECG) parameters to be summarized include heart rate, PR, QT, QTcF and QRS.

Population	Description
Enrolled	All participants who sign the informed consent document.
Full analysis set (FAS)	All participants randomly assigned to study intervention and who take at least 1 dose of study intervention. Participants will be analyzed according to the treatment arm they are randomized to.
Safety	All participants randomly assigned to study intervention and who take at least 1 dose of study intervention. Participants will be analyzed according to the treatment they actually received.
Substudy analysis set (SAS)	All participants who entered the substudy and who take at least 1 dose of study intervention during the substudy.

## 4. ANALYSIS SETS (POPULATIONS FOR ANALYSIS)

For safety analyses, participants will be analyzed according to the treatment they actually received. On the other hand, for efficacy analyses, participants will be analyzed according to the treatment arm they are randomized to.

## **5. GENERAL METHODOLOGY AND CONVENTIONS**

The study will be analyzed and reported once all randomized participants have completed all scheduled procedures (or discontinued) in the main study, i.e. at study participant data set release after the completion of the main study. The substudy will be analyzed and reported after the substudy data set release following last participant last visit in the substudy. The substudy report will include analyses that are discussed in Sections 6.1 (using the SAS), 6.3, 6.5, and Appendix 2.5.

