Height SDS and fracture rates have been previously assessed in adolescent participants in order to assess whether the microscopic, transient nonclinical finding in rats translated to changes in adolescent bone growth and development. HT SDS is the standard for measuring changes in height in clinical trials as it allows efficient use of data across both ages and genders.²³ In the safety update data, including B7451036, at each dose and time point where the HT SDS was assessed the median change was 0, suggesting that participants remain on the growth curve that had been established prior to abrocitinib dosing. Fracture rates is a PFIZER CONFIDENTIAL

Page 98

relevant measure for assessment of a clinically meaningful impact on bone. Fracture rates are high in adolescence because there is a lag in mineralization relative to bone lengthening.²⁴ The fracture rates in adolescent participants in the safety update data, including B7451036, representing an IR of 0.92/100 (CI, 0.25, 2.35) patient years. To contextualize the rate of fractures in the abrocitinib development program, the IR of fracture in a large Danish Health Registry (3,909 patients with AD aged 12 to <18) was 2.72/100 PY (272.19/10,000 PY) [Danish Report Table 15].

This substudy will provide imaging data to further evaluate whether abrocitinib has any potential effects on adolescent bone with regard to bone safety findings in knee MRI, including to assess if there is any abrocitinib-associated effects on cartilage mineralization in the actively growing bones of adolescent participants with moderate to severe AD and to verify that epiphyseal plate closure occurs as expected in late adolescence or early adulthood. Findings of the substudy will further inform risk assessment as to whether administration of abrocitinib may affect bone in adolescents.

Knee MRI is the selected imaging modality and body site utilized in the substudy for several reasons:

- The spatial resolution for MRI provides the best opportunity to identify morphologic changes that may be related to abrocitinib exposure.
- MRI permits visualization of the ossification centers and verification of epiphyseal plate closure.
- MRI does not require ionizing radiation exposure for adolescent participants.

The knee is a suitable body site to evaluate because there are 3 ossification centers.

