10.10.6. Substudy Study Treatments

There are no additional requirements for the substudy and the requirements from the main study apply, except that adolescent participants who enter the substudy will continue to receive study intervention as assigned in the main study after the 12-week treatment period, until 1 year after randomization in the main study or until they turn 18 years of age. Participants will be dispensed bottles of study intervention at Week 12, Week 24 and Week 36 visits. Please refer to the Study Intervention(s) and Concomitant Therapy section (Section 6) of the main protocol for further details.

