10.10.7.2. Substudy Early Termination/End of Treatment Visit

• A Substudy End/Early Termination Visit will be performed approximately within 1 month of the participant turning 18 years of age, OR whenever the participant discontinues from the substudy, OR 1 year after participant randomization in the main study; whichever is the sooner.

• An MRI should be arranged approximately within 1 month of the visit (but must be AFTER the participant has turned 18 years of age if participant is completing substudy due to turning 18).

- After the MRI is performed, review if any abnormal knee MRI findings then:
 - Review findings identified by central reader MRI evaluation, and (if relevant) the adjudication report, and arrange any further follow-up and investigation, if relevant and required;
 - Record medical history/adverse event/laboratory assessment abnormality as appropriate.

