10.10.7.4. Substudy Discontinuation Criteria

A participant will be discontinued from the substudy and have a Substudy Early

Termination/End of Treatment Visit if:

- The participant meets any of the discontinuation criteria of the main B7451094 study;
- If the participant is no longer an active participant of the main B7451094 study;
- If the participant has turned 18 years of age during the substudy.

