#### PFIZER GENERAL BUSINESS

# Figure 1. Study Design (Main Study)

# **3. ENDPOINTS AND BASELINE VARIABLES: DEFINITIONS AND CONVENTIONS**

## 3.1. Primary Endpoint(s)

The primary endpoint is the incidence of AEs/SAEs, defined as the number of participants with treatment emergent adverse events, divided by the number of participants in the Safety Population (Section 4).

An adverse event will be considered treatment emergent relative to a given treatment if:

• The event starts on or after the first dose of study drug, but before the last dose plus the lag time of 28 days. The algorithm will not consider any events that started prior to the first dose date. If an AE starts on the same day as the first dose date, it will be considered treatment emergent.

or

• The event was seen prior to the start of study drug but increased in severity during the effective duration of treatment.

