## 5.2. General Methods

## 5.2.1. Analyses for Binary Endpoints

Binary endpoints (response based on IGA, EASI-75 and SCORAD75 and incidence of bone safety findings) will be presented using proportions together with the 95% confidence

PFIZER GENERAL BUSINESS

interval calculated using the normal approximation (or the Clopper-Pearson exact method when the estimated proportion is 0 or 1). Incidence of adverse events will be presented using frequency counts and percentages.

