## 6. ANALYSES AND SUMMARIES

## **6.1.** Primary Endpoint(s)

## 6.1.1. Incidence of AEs/SAEs

- Estimand strategy: Treatment policy (Section 2.1.1).
- Analysis set: Safety (Section 4).
- Analysis methodology: Descriptive statistics.
- Intercurrent events and missing data: All adverse event data collected will be analyzed regardless of dosing compliance or treatment discontinuation; missing values will not be imputed.
- The number and proportion of participants who had treatment emergent adverse events will be presented for each treatment arm. Treatment emergent adverse events will be summarized according to type, frequency, severity, seriousness and relationship to abrocitinib in each treatment arm.

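### The one-year adolescent substudy reports adverse events only as crude proportions although time at risk is unequal by design; define the AE window and add rates per 100 patient-years

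*SAP*

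**What the plan says.** SAP Section 5 lists the content of the substudy report: "The substudy report will include analyses that are discussed in Sections 6.1 (using the SAS), 6.3, 6.5, and Appendix 2.5". Section 6.6 is not on that list.

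The AE method comes from SAP 6.1.1: "The number and proportion of participants who had treatment emergent adverse events will be presented for each treatment arm". SAP 5.2.1 confirms the form: "Incidence of adverse events will be presented using frequency counts and percentages". The SAP has no rate per patient-year and no time-to-event analysis of AEs.

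Follow-up is unequal by design. Protocol 10.10.6 continues treatment "until 1 year after randomization in the main study or until they turn 18 years of age". Protocol 10.10.7.4 lists as a reason to discontinue: "If the participant has turned 18 years of age during the substudy". Protocol 10.10.7.2 sets the end visit at about the 18th birthday, or "whenever the participant discontinues from the substudy, OR 1 year after participant randomization in the main study; whichever is the sooner".

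Two AE windows are in play. SAP 3.1 counts events starting from first dose "but before the last dose plus the lag time of 28 days". SAP 6.1.1 cites the estimand in SAP 2.1.1, which counts events up to Week 16. Neither is restated for the substudy.

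SAP 6.5.3 summarises exposure and is part of the substudy report, but its top category is 10 weeks or more.

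As background, Protocol 10.10.1.1 gives adolescent fracture rates per 100 patient-years: the programme figure, "representing an IR of 0.92/100 (CI, 0.25, 2.35) patient years", and 2.72 from a Danish registry.

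**The concern.** A crude percentage gives every treated participant the same weight in the denominator, whether that person was at risk for 16 weeks or for 13 months. That is harmless when nearly everyone has the same window, as in the 12-week main study. In the substudy it mixes event risk with length of follow-up. Read as a one-year figure, the percentage can be too low. If discontinuation differs between 100 mg and 200 mg, the side-by-side display also mixes dose with time at risk.

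This is the trial's only one-year adolescent safety data. The planned output is also not on the person-time scale that the protocol uses when it discusses adolescent fractures. The exposure table will not show the spread either, because almost everyone treated beyond the main study falls into its last category.

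**Working it through.** **1. The protocol's own figures.** With exact Poisson limits, 4 events (inferred, not stated) in 435 patient-years (PY) give 4/435 = 0.92 per 100 PY. The lower limit is χ²(0.025; 8 df)/2/435 = 0.25 and the upper limit is χ²(0.975; 10 df)/2/435 = 2.35, as stated. At the same rate, 3 events would give 0.19 to 2.69 and 5 events 0.30 to 2.15, so neither fits. Registry: 272.19 per 10,000 PY = 2.72 per 100 PY.

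**2. Planned time at risk.** A one-year completer has 365 + 28 = 393 days (1.077 years). The substudy schedule gives participants who turn 18 during the main study a baseline MRI only; I read this as completing the 12 weeks, so 84 + 28 = 112 days (0.307 years, 16 weeks). Anything shorter needs dropout.

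**3. Assumptions, none of them in the documents.** Age at entry is uniform over the stated range. The event hazard is constant. Dropout is exponential, with the stated percentage stopping within a year and the 28-day lag still counted. All adolescents dosed from Day 1 are in the substudy analysis set.

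**4. Crude proportion against a true one-year risk of 60%.** The hazard is λ = −ln(1 − 0.60) = 0.916 per year. The chance of an event is 1 − exp(−λt): 24.5% by 112 days and 62.7% by 393 days. It averages 45.8% for those whose window is spread evenly between the two.

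- Ages 12 to <18, no dropout: 3.8% turn 18 within 12 weeks, 12.8% between then and one year, and 83.3% complete. The result is 0.038 × 24.5 + 0.128 × 45.8 + 0.833 × 62.7 = 59.1%.
- Ages 16 to <18, no dropout: 0.115 × 24.5 + 0.385 × 45.8 + 0.500 × 62.7 = 51.8%.

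Simulation with dropout added gives the following, with mean years at risk in brackets:

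| Ages | No dropout | 20% | 30% |
|---|---|---|---|
| 12 to <18 | 59.1% (0.998) | 54.6% (0.905) | 52.2% (0.856) |
| 15 to <18 | 55.5% (0.919) | 51.5% (0.838) | 49.3% (0.794) |
| 16 to <18 | 51.8% (0.840) | 48.3% (0.770) | 46.4% (0.733) |

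For a true 30%, the corresponding range is about 30% down to 22%.

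**5. If the Week 16 window applied instead.** Week 16 is day 112, so follow-up would be nearly equal and this bias would largely vanish. But under the same hazard only 24.5% would have an event by then, and everything later in the year would fall outside the measure.

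**6. Fractures.** The substudy size is not stated. As an illustration, 27 PY (about 30 adolescents at about 0.9 years each) would yield 27 × 0.0092 = 0.25 expected fractures at the programme rate and 27 × 0.0272 = 0.73 at the registry rate. With none seen, the upper 95% limit is −ln(0.025)/27 = 3.689/27 = 13.7 per 100 PY.

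**The case against.** The strongest reply is that the plan never sets a one-year AE risk as its target. SAP 5.1 calls the study descriptive, the primary estimand covers 16 weeks, and the substudy's primary endpoint is adjudicated MRI findings. A count and percentage labelled as covering the observed period is not biased for what it describes. This stands: the shortfall arises only when the figure is read as a one-year risk, which a one-year substudy report invites but does not state.

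A reader might infer that the age-18 stop by itself makes the result materially too low. The documents do not support that. Completers are counted for 393 days, and this offsets the loss from those turning 18: with uniform ages and no dropout, mean time at risk is 0.998 years. Material bias needs dropout or an older cohort.

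A reader might also infer that the substudy AEs cannot be compared with the fracture rates. That is too strong. The protocol gives those rates as context for the existing programme and plans no comparison. If SAP 6.5.3 shows means or totals, an approximate denominator exists. For a rare event over about a year the two scales nearly agree: at 2.72 per 100 PY, uniform ages and no dropout, the crude figure is about 2.7%. Any comparison would be imprecise in either form.

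The last objection is that the window conflict comes first, since no rate can be defined until it is settled. That is right, and the fix is ordered accordingly.

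**Conclusion.** The point holds as a gap in method, with a size that depends on facts the documents do not give. Substudy AEs are crude proportions over unequal planned follow-up, no person-time measure is planned, and the AE window is not defined for the substudy. For a true one-year risk of 60%, the relative shortfall is (60 − 59.1)/60 = 1.5% in the most favourable case shown and (60 − 46.4)/60 = 23% in the least favourable.

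These figures rest on uniform ages, a constant hazard, exponential dropout, and my reading that participants turning 18 in the main study complete its 12 weeks. If AEs cluster early in treatment, the shortfall is smaller. The fracture rates support the choice of scale only; they are no evidence of a failed comparison.

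**What to change.** For the substudy analysis set, in SAP 5, 6.1.1 and 6.5.3:

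1. State that the substudy AE window is first dose to last dose plus 28 days, as in SAP 3.1, and not the Week 16 window of the estimand that 6.1.1 cites.
2. Beside the crude counts, report first-event incidence rates per 100 patient-years by arm: participants with the event, divided by summed time to first event or end of window, with exact Poisson 95% CIs. Do this for any TEAE, SAEs, serious infections and fractures. Name the last two explicitly, because serious infections are summarised in SAP 6.6.1, outside the substudy list, and fractures are not specified at all. If a one-year risk is wanted, add a time-to-first-event estimate.
3. Extend the exposure categories beyond 10 weeks to one year, and report total patient-years by arm.

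The cost is SAP wording and one extra table. AE and dosing dates are already collected, and nothing changes in conduct. Intervals for rare events will be wide, but they show how little a zero count establishes, which a bare 0% without limits does not.

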c. Participants who turn 18 years during the main study will only have baseline MRI. Participants who have completed 3 months of treatment in the main study and turn 18 years of age during the substudy will be required to attend an early termination visit with an MRI scan.

d. AEs and SAEs are recorded/reported as per Section 8.3.

e. Visits corresponding to main visits. Week 12 visit is End of treatment visit for main study. For substudy participants, activities will be performed as per the substudy schedule of activities.

f. Clinical chemistry includes: urea, sCr, sCysC (at Screening only), estimated creatinine clearance, AST, ALT, TBili, alkaline phosphatase. The lipid profile will include total cholesterol, LDL, VLDL, HDL, and triglycerides. Hematology includes: hemoglobin, WBC, neutrophils (%, absolute), lymphocytes (%, absolute), platelets, and coagulation panel (APTT, PT/INR). Laboratory tests with abnormal results may be repeated once during the screening period; the last value will be used to determine eligibility. Fasting lipid profile panel require at least an 8 hour fast. If possible, participants should comply with fasting requirements at those visits detailed above. For all adolescent participants for the substudy, laboratory tests will be performed at Screening, Week 4 and Week 12 as per the main study SoA, as well as at the ET/EOT visit of the substudy.

g. Review and record contraceptive method and results of pregnancy testing. Confirm that the participant is adhering to the contraception method(s) required in the protocol. Refer to Appendix 4 for contraceptive guidance.

Primary substudy objective(s):		Primary substudy endpoint (as secondary endpoints for B7451094):	
•	To evaluate the potential effects of abrocitinib on bone development in adolescent participants 12 to <18 years of age, as assessed by knee MRI.	•	The proportion of bone safety findings in knee MRI 1 year after randomization in adolescent participants exposed to abrocitinib 100 mg and 200 mg QD.

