## 6.5.3. Study Treatment Exposure

A summary of dosing compliance by treatment arm will be provided. Dosing compliance will be calculated as the percent of the number of doses of study drug the participant took out of the expected total number of doses. Number and percent of participants with compliance of < 80 % and > 120% will be provided for each treatment arm.

The exposure to study drug (computed as last dosing date – first dosing date + 1) will be summarized by treatment arm and according to duration categories (<1 week,  $\geq$ 1 week to <4 weeks,  $\geq$ 4 weeks to < 8 weeks,  $\geq$ 8 weeks to < 10 weeks, and  $\geq$ 10 weeks).

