## 6.6. Safety Summaries and Analyses

All safety analyses will be performed on the Safety population. These will be presented in a tabular format and summarized descriptively for each treatment arm following Pfizer standards as appropriate.

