## PFIZER GENERAL BUSINESS

emergent AEs/SAEs, withdrawal from active treatment due to AEs, and serious infections, defined as any infection (viral, bacterial, and fungal) requiring hospitalization or parenteral antimicrobials or meets other criteria that require it to be classified as a serious adverse event.

Any AEs that occur after signing Informed Consent and before randomization and the first dose of study drug will be listed but not summarized.

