# 6.6.2. Laboratory Data

Laboratory data will be listed and summarized according to CaPS. Laboratory parameters will be summarized descriptively at baseline, Week 4 and EOT visits, and will include the observed and change from baseline values.

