## 6.6.3. Vital Signs

Vital signs will be summarized descriptively over time. Summaries will include the observed and change from baseline values. Height and weight will be summarized at baseline.

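### The substudy report omits SAP Section 6.6, so laboratory and vital-sign data after Week 12 are assigned to no report; separately, the exposure bands stop at 10 weeks or more

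*SAP*

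**What the plan says.** SAP Section 5 plans two reports. For the main one, "The study will be analyzed and reported once all randomized participants have completed all scheduled procedures (or discontinued) in the main study". The second follows the last substudy visit, and its content is listed: "The substudy report will include analyses that are discussed in Sections 6.1 (using the SAS), 6.3, 6.5, and Appendix 2.5". SAS here is the substudy analysis set.

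Section 6.6 holds the safety tables beyond the primary AE analysis, and it names one population: "All safety analyses will be performed on the Safety population". Within it:
- 6.6.1 adds AE summaries that include "emergent AEs/SAEs, withdrawal from active treatment due to AEs, and serious infections". A serious infection is defined there to include one needing hospitalization or parenteral antimicrobials.
- 6.6.2: "Laboratory parameters will be summarized descriptively at baseline, Week 4 and EOT visits".
- 6.6.3: "Vital signs will be summarized descriptively over time".

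The substudy schedule (Protocol 10.10.2) marks vital signs at every visit, which after Week 12 means Weeks 24 and 36, ET/EOT and follow-up. Footnote f sets laboratory tests at Screening, Week 4 and Week 12, "as well as at the ET/EOT visit of the substudy".

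Section 6.5.3, which is in the substudy list, has exposure "summarized by treatment arm and according to duration categories". The highest category is 10 weeks or more.

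**The concern.** Only adolescents are treated beyond 12 weeks in this trial, so the substudy is its only source of longer-term safety data. Protocol 2.3.1 names falls in lymphocytes and platelets and changes in lipids as risks, and relies on monitoring throughout the study to mitigate them. Protocol 10.10.10 leaves the analysis of substudy data to the SAP. If the SAP assigns the late laboratory and vital-sign data to no report, they can be collected, cleaned and never tabulated by arm. Any later table would then be a post hoc choice.

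The exposure bands are a separate matter. The bone endpoint concerns findings after a year of exposure, and a reader will want to know how many adolescents were actually treated that long.

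**Working it through.** The plan states no figure on this point. The check sets the report list against the section contents and the substudy schedule.

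**1. Where each late item is analyzed**

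| Data after Week 12 | Collected (Protocol 10.10.2) | SAP section | In substudy list? |
|---|---|---|---|
| Laboratory values | ET/EOT | 6.6.2 only | No |
| Vital signs | Weeks 24, 36, ET/EOT, follow-up | 6.6.3 only | No |
| Serious infections as a defined category | Continuous AE collection | 6.6.1 only | No |
| Withdrawals due to AEs, dedicated summary | Continuous AE collection | 6.6.1 only | No |
| All treatment-emergent AEs and SAEs | Continuous AE collection | 6.1 | Yes, on the SAS |
| Discontinuations | Disposition data | 6.5.2 | Yes |
| ECG | Not scheduled in the substudy | 6.6.4 | Not needed |

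**2. Whether the main report picks up the first two rows.** Footnote e of the substudy schedule calls Week 12 the end-of-treatment visit of the main study, and the main report is tied to main-study completion. EOT in 6.6.2 therefore most naturally means Week 12. Some adolescents randomized early may have later visits in the database by then, but the SAP does not say these would be used, and coverage would depend on enrolment dates. The substudy windows in SAP Appendix 2.1 serve only MRI and HSS Pedi-FABS, and Weeks 24 and 36 have none.

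**3. Count of affected time points per participant**
- Laboratory: Screening, Week 4, Week 12 and ET/EOT make 4 scheduled time points; 1 is unassigned.
- Vital signs: 4 visits after Week 12 are unassigned, and fewer for anyone who stops or turns 18 early.

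**4. Adverse-event window.** SAP 3.1 counts events up to the last dose plus 28 days. With a last dose at about Day 366, the window ends at 366 + 28 = Day 394. AEs and SAEs through the treatment year are therefore within 6.1 on the SAS.

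**5. Exposure bands.** The top band starts at 10 × 7 = 70 days. Courses of 84, 168, 252 and 365 days (12, 24 and 36 weeks, and one year) all exceed 70, so all four fall in one category. For a one-year course, 365 − 70 = 295 days, or 295/365 = 81%, lie above the last boundary.

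**The case against.** The case against has real force on several points.

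- **Serious infections.** A reader might infer that they fall in no planned analysis. The documents do not support that. Section 6.1 on the SAS tabulates treatment-emergent events by type and seriousness through the window in step 4. What is lost is the defined category: an infection that needed parenteral antimicrobials but was not reported as an SAE could not be picked out.
- **Withdrawals due to AEs.** Discontinuation is summarized under 6.5.2. That section defers to sponsor standards and does not spell out reasons, so only the dedicated 6.6.1 table is clearly missing.
- **Size of the gap.** A reader might divide the days from Day 85 to Day 366 by a year (281/365 = 77%) and call that the share of data lost. It measures calendar time. Only one scheduled laboratory time point is affected, and participants who turn 18 do not have a full year.
- **Clinically important changes.** Protocol 8.2.5 and 10.3.1 have the investigator record these as AEs, so they reach 6.1. Routine change-from-baseline tables are what is missing.
- **Exposure.** Section 6.5.3 can be read as also giving a continuous summary, with the statistics in 5.2.2, and that would show the range. The weakness is then confined to the categories. It is unrelated to the laboratory and vital-sign gap.
- **Scope.** The substudy endpoint is bone findings, and the report list does not say that nothing else may be added.

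Two further defences do not close the gap. Reading EOT in 6.6.2 and the open wording of 6.6.3 as covering substudy visits conflicts with the report timing and with the omission of 6.6. The additional interim summaries in SAP 7.1 are optional.

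**Conclusion.** The omission holds, within limits. If the SAP is followed as written, the ET/EOT laboratory results (one time point per participant) and the vital signs at up to four visits after Week 12 are summarized in neither report. The dedicated serious-infection and AE-withdrawal summaries are not carried into the substudy report. Separately, the exposure categories cannot distinguish 12 weeks from one year.

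The primary endpoint, the year-long AE and SAE tables and the MRI analysis are unaffected. This should be corrected, but it does not undermine the study.

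The conclusion rests on three readings:
- The Section 5 list is taken as the planned content of the report.
- EOT in 6.6.2 is taken as Week 12.
- Section 6.1 on the SAS is taken to use the window in SAP 3.1, not the Week 16 limit of the main-study estimand in 2.1.1. That limit falls at about Day 113 (16 × 7 + 1) and would leave later AEs out as well.

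The documents do not give the number of adolescents or how many will complete a year, so the number of participants affected cannot be stated.

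**What to change.** Amend the SAP as follows:

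1. In Section 5, add 6.6.1 to 6.6.3 (using the SAS) to the substudy report list, and let the opening sentence of 6.6 allow that population.
2. In 6.6.2, name the substudy ET/EOT visit. In 6.6.3, name Weeks 24 and 36, ET/EOT and follow-up. State whether nominal visits or windows apply, since Appendix 2.1 has none for these data.
3. In 6.5.3, extend the duration bands to one year for the substudy report, for example 12 to <24, 24 to <36, 36 to <48, and 48 weeks or more, with the lower bands adjusted to meet them.

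ECG need not be added, because the substudy schedule has none.

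The cost is a few lines of SAP text and a few extra descriptive tables. No new data collection is needed, and no protocol endpoint changes.
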